6.5.2.1 Criteria for Hematologic and Nonhematologic Recovery

- Absolute neutrophil count (ANC) must be $\geq 1 \times 10^9/L$
- Platelet count must be $\geq 75 \times 10^9/L$
- All other nonhematologic toxicity (except for alopecia) must have resolved to \leq Grade 1 or to the patient's baseline condition

6.6 Criteria for Dose Modification (Delays, Reductions, and Discontinuations)

When possible, toxicities should be attributed to a specific study drug (MLN9708 or dexamethasone [as applicable]) so that dose modifications can be made rationally. If multiple toxicities are noted, the dose adjustments and/or delays should be made once per cycle according to the most severe toxicity guidelines.

6.6.1 MLN9708 Dose Adjustments for Hematologic Toxicity

Dosage adjustments for hematologic toxicity are outlined in [Table 6-2](#).

Table 6-2 MLN9708 Dose Adjustments for Hematologic Toxicities

Criteria	Action
Within-Cycle Dose Modifications	
If platelet count $\leq 30 \times 10^9/L$ or ANC $\leq 0.75 \times 10^9/L$ on a MLN9708 dosing day (other than Day 1)	MLN9708 dose should be withheld. Complete blood count (CBC) with differential should be repeated at least every other day until the ANC and/or platelet counts have exceeded the prespecified values (see Section 6.5.2.1) on at least 2 occasions. In the event CBC cannot be repeated at least every other day, dose modifications should be made in consultation with sponsor. Upon recovery, MLN9708 may be reinitiated with 1 dose level reduction or by 33% if the patient is receiving the first dose level.
Dose Modifications for Subsequent Treatment Cycles	
Delay of > 2 weeks in the start of a subsequent cycle due to lack of toxicity recovery as defined in Section 6.5.2 :	
 - Hold MLN9708 until resolution as per criteria Section 6.5.2. - Reduce MLN9708 1 dose level or 33% if the patient is receiving the first dose level. - The maximum delay before treatment should be discontinued (except in the case of investigator determined clinical benefit and discussion with the Millennium clinician) will be 3 weeks.
Dose Modifications for Subsequent Treatment Cycles	
All hematologic toxicities	For hematologic toxicity that occurs during a cycle but recover in time for the start of the next cycle, a dose level reduction will be made either based on within-cycle or for

Table 6-2 MLN9708 Dose Adjustments for Hematologic Toxicities

Criteria	Action
	subsequent cycle criteria, but not for both from the same cycle.

6.6.2 MLN9708 Dose Adjustments for Nonhematologic Toxicity

Dosage adjustments for nonhematologic toxicity are outlined in [Table 6-3](#).

Table 6-3 MLN9708 Dose Adjustments for Nonhematologic Toxicities

Criteria	Action
Peripheral Neuropathy:	
Newly developed Grade 1 peripheral neuropathy with pain, Grade 2 peripheral neuropathy,	Reduce dose of MLN9708 to the previous dose level or by 33% if the patient is receiving the first dose level.
Grade 2 neuropathy with pain or Grade 3 peripheral neuropathy	Hold MLN9708 until toxicity resolves or returns to baseline. When toxicity resolves, re-initiate MLN9708 at the previous dose level or by 33% if the patient is receiving the first dose level.
Grade 4 peripheral neuropathy	Discontinue MLN9708.
Peripheral neuropathy should be monitored until toxicity resolves or returns to baseline. Upon toxicity recovery, if the patient has received clinical benefit from therapy with MLN9708, the investigator and Millennium clinician may consider restarting therapy.	
All Other Grade \geq 3 Nonhematological Toxicities, except:	
- \geq Grade 3 nausea and/or vomiting in the absence of optimal anti-emetic prophylaxis (Section 6.10)	- Hold MLN9708 until resolution to Grade < 1 or baseline.
- \geq Grade 3 diarrhea that occurs in the absence of optimal supportive therapy (Section 6.10)	- Reduce MLN9708 1 dose level or 33% if the patient is receiving the first dose level.
- Grade 3 fatigue	- Note, a dose level reduction will be made either based on within-cycle or for a subsequent cycle criteria, but not for both from the same cycle.
Grade 4 Nonhematologic Toxicities	
	Consider permanently discontinuing MLN9708. Exception, in the case where the investigator determines the patient is obtaining a clinical

Table 6-3 MLN9708 Dose Adjustments for Nonhematologic Toxicities

Criteria	Action
	benefit and has discussed this with the Millennium clinician.
Criteria for Retreatment and Cycle Delays	
Both hematologic & nonhematologic recovery required	
Delay therapy \times 1 week.
 
Re-evaluate patient; if still not resolved, delay therapy \times 1 additional week.

If not resolved	
If initiation of subsequent therapy needs to be delayed for more than 2 weeks because of incomplete recovery from treatment related toxicity, the dose of MLN9708 will be reduced by at least 1 dose level when treatment resumes.
 
The maximum delay before treatment should be discontinued (except in the case of investigator-determined clinical benefit and discussion with the Millennium clinician) will be 3 weeks.

6.6.3 Dexamethasone-Related Treatment Modification

Dosage adjustments for dexamethasone are outlined in [Table 6-4](#). Dexamethasone dose treatment modifications are outlined in [Table 6-5](#).

Table 6-4 Dose Reduction Steps for Dexamethasone

Starting Dose	First Dose Reduction	Second Dose Reduction	Third Dose Reduction
40 mg QD	20 mg QD	8 mg QD	Discontinue dexamethasone

Table 6-5 Dexamethasone-Related Treatment Modification (Delays, Reductions, and Discontinuations) Guidelines Due to Adverse Events

Adverse Event (Severity)	Action on Study Drug
Gastrointestinal Dyspepsia, gastric, or duodenal ulcer, gastritis Grades 1-2 (requiring medical management)	Treat with histamine-2 blockers, sucralfate, or omeprazole. If symptoms persist despite these measures, decrease dexamethasone by 1 dose level.
> Grade 3 (requiring hospitalization or surgery)	Hold dexamethasone until symptoms adequately controlled. Restart and decrease 1 dose level of current

Table 6-5 Dexamethasone-Related Treatment Modification (Delays, Reductions, and Discontinuations) Guidelines Due to Adverse Events

Adverse Event (Severity)		Action on Study Drug
		dose along with concurrent therapy with histamine-2 blockers, sucralfate, or omeprazole. If symptoms persist despite these measures, discontinue dexamethasone and do not resume.
	Acute pancreatitis	Discontinue dexamethasone and do not resume.
Cardiovascular	Edema > Grade 2 (limiting function and unresponsive to therapy or anasarca)	Diuretics as needed and decrease dexamethasone by 1 dose level. If edema persists despite these measures, decrease dose another level. Discontinue dexamethasone and do not resume if symptoms persist despite second reduction.
Neurological	Confusion or mood alteration > Grade 2	Hold dexamethasone until symptoms resolve. Restart with 1 dose level reduction. If symptoms persist despite these measures, discontinue dexamethasone and do not resume.
Musculoskeletal	Muscle weakness > Grade 2 (interfering with function ± interfering with activities of daily living)	Decrease dexamethasone dose by 1 dose level. If weakness persists despite these measures, decrease dose by 1 dose level. Discontinue dexamethasone and do not resume if symptoms persist.
Metabolic	Hyperglycemia > Grade 3 or higher	Treatment with insulin or oral hypoglycemics as needed. If uncontrolled despite these measures, decrease dose by 1 dose level until levels are satisfactory.

Source: Package insert for DEXAMETHASONE Tablets USP, DEXAMETHASONE Oral Solution September 2007, Roxane Laboratories, Inc, a division of Boehringer Ingelheim.⁽⁵⁹⁾

6.7 Excluded Concomitant Medications and Procedures

The following medications and procedures are prohibited during the study.

Systemic treatment with any of the following metabolizing enzyme inhibitors is not permitted during this study. The rationale for this is that in the event of a drug-drug interaction with an inhibitor, MLN9708 exposure would be increased leading to a high probability of an AE.

- Strong inhibitors of CYP1A2: fluvoxamine, enoxacin, ciprofloxacin
- Strong inhibitors of CYP3A: clarithromycin, telithromycin, itraconazole, voriconazole, ketoconazole, nefazodone, and posaconazole

Systemic treatment with any of the following metabolizing enzyme inducers should be avoided, unless there is no appropriate alternative medication for the patient's use. The rationale for this (unlike with inhibitors) is that in the event of a drug-drug interaction with an inducer, MLN9708 exposure would be decreased, leading to a reduced chance of toxicity and potentially a reduced chance of efficacy.

- Strong CYP3A inducers: rifampin, rifapentine, rifabutin, carbamazepine, phenytoin, and phenobarbital
- ACE inhibitors (ACE inhibitors should be used with caution and requires consultation with the Millennium clinician. Patients with AL amyloidosis usually poorly tolerate ACE inhibitors, not due to possible interaction with MLN9708, but because of symptomatic hypotension due to an underlying involvement of the autonomic nervous system. Therefore, ACE inhibitors should be excluded in patients with eGFR < 60mg/min/1.72 and in those whom orthostatic systolic blood pressure is < 100 mmHg.)
- Excluded foods and dietary supplements include St. John's wort and Ginkgo biloba
- Warfarin (aspirin is allowed)

The following procedures are prohibited during the study:

- Any antineoplastic treatment with activity against AL amyloidosis, other than study drugs

- Radiation therapy (note that, in general, the requirement for local radiation therapy indicates disease progression)
- Platelet transfusions to help patients meet eligibility criteria are not allowed within 3 days prior to study drug dosing

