Metabolism appears to be the major route of elimination for MLN2238 and urinary excretion of the parent drug is negligible (< 3% of dose). In vitro studies indicate that MLN2238 is metabolized by multiple cytochrome P₄₅₀s (CYPs) and nonCYP enzymes/proteins. The rank order of relative biotransformation activity of the 5 major human cytochrome P450 (CYP) isozymes was 3A4 (34.2%) > 1A2 (30.7%) > 2D6 (14.7%) > 2C9 (12.1%) > 2C19 (< 1%). All metabolites observed in the human liver microsome studies were also found in the rat and dog, supporting the rat and dog as the species to be used for toxicology studies. MLN2238 is not an inhibitor of CYPs 1A2, 2C9, 2C19, 2D6, or 3A4 ($IC_{50} > 30 \mu\text{M}$, estimated $K_i > 15 \mu\text{M}$) nor a time-dependent inhibitor of CYP3A4/5 (up to 30 μM). The potential for MLN9708 treatment to produce drug-drug interactions (DDI) via CYP inhibition is inferred to be low. However, there may be a potential for DDIs with a concomitant strong CYP3A4 or CYP1A2 inhibitor because of the potential for first-pass metabolism when MLN2238 is administered via the PO route, and because of the moderate contribution of CYP3A4- and CYP1A2-mediated metabolism of MLN2238 in human liver microsomes. To ensure patient safety and minimize PK variability in this first-in-human

investigation of the PO formulation of MLN9708, strong inhibitors of CYPs 3A and 1A2 and strong CYP3A inducers are identified as excluded concomitant medications.

MLN2238 may be a weak substrate of P-glycoprotein (P-gp), breast cancer resistance protein (BCRP), and multidrug resistance associated protein (MRP2) efflux pump transporters. MLN2238 is not an inhibitor of P-gp, BCRP, and MRP2 ($IC_{50} > 100 \mu M$). The potential for DDI with substrates or inhibitors of P-gp, BCRP, and MRP2 is therefore inferred to be low.

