- b. Previous or ongoing psychiatric illness and/or social situations that would limit compliance with study requirements.

9. Systemic infections:

- a. Known to be human immunodeficiency virus (HIV)-positive.
- b. Known to be hepatitis B surface antigen-positive or has known or suspected active hepatitis C infection.
- c. Uncontrolled infection requiring systemic antibiotics.

10. Other malignant disease/s:

- a. Clinically overt multiple myeloma (bone marrow plasma cells \geq 30%), and at least 1 of the following: bone lesions, anemia (< 100 g/L), and hypercalcemia.
- b. Patients with amyloidosis due to mutations of the transthyretin gene (see Section 15.2).
- c. Patients with non-AL amyloidosis (see Section 15.2).
- d. Presence of other active malignancy with the exception of nonmelanoma skin cancer, cervical cancer, treated early-stage prostate cancer provided that prostate-specific antigen is within normal limit, or any completely resected carcinoma in situ.

11. Female patients who are lactating or pregnant.

12. Major surgery within 14 days before the first dose of study drug.

13. Systemic treatment with strong inhibitors of CYP1A2 (fluvoxamine, enoxacin, ciprofloxacin), strong inhibitors of CYP3A (clarithromycin, telithromycin, itraconazole, voriconazole, ketoconazole, nefazodone, posaconazole) or strong CYP3A inducers

(rifampin, rifapentine, rifabutin, carbamazepine, phenytoin, phenobarbital), or use of Ginkgo biloba or St. John's wort within 14 days before the first dose of study treatment.

14. Any other serious medical or psychiatric illness that could, in the investigator's opinion, potentially interfere with the completion of treatment according to this protocol.

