- Other MLN9708-related nonhematologic toxicities Grade 2 or greater that, in the opinion of the investigator, requires discontinuation of therapy with MLN9708.

[figure not shown]
Patients who do not receive all doses of MLN9708 in Cycle 1 for reasons other than DLTs will be replaced within the cohort. Patients who receive all doses of MLN9708, yet for unforeseen circumstances recovery of toxicity is not available and safety in Cycle 1 cannot be fully evaluated may be replaced within the cohort.

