8.1.3 Populations for Analysis

The populations used for analysis will include the following:

Safety Population: Patients who receive at least 1 dose of MLN9708. The safety population will be used for safety analyses.

DLT-evaluable Population: Patients who receive all Cycle 1 doses of MLN9708 or experience a DLT in Cycle 1. The DLT-evaluable population will be used to determine the MTD.

Organ Response-Evaluable Population: The organ response-evaluable population is defined

as patients who receive at least 1 cycle of MLN9708, have amyloid involvement of at least kidney or heart at baseline, and at least 1 post-baseline organ response assessment.

Hematologic Response-Evaluable Population: The hematologic response-evaluable population is defined as patients who receive at least 1 cycle of MLN9708, have measurable disease at baseline, and at least 1 post-baseline hematologic response assessment.

Plasma PK Analysis Population: Patients who:

- a. Receive full doses of MLN9708 during Cycle 1 without dose reduction or interruptions through the completion of PK sampling
- b. Do not receive any excluded concomitant medications
- c. Have sufficient plasma MLN2238 concentration-time data to permit reliable estimation of plasma PK parameters

Pharmacodynamic Analysis Population: Patients who:

- a. Receive full doses of MLN9708 during Cycle 1 without dose reduction or interruptions
- b. Do not receive any excluded concomitant medications through the completion of pharmacodynamic sampling
- c. Have sufficient whole blood 20S proteasome inhibition-time data to permit reliable estimation of pharmacodynamic parameters

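### Section 6.7 allows a strong CYP3A inducer that Section 1.2.2 excludes, and a patient who starts one in Cycle 1 without a DLT still counts toward the MTD

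*Protocol*

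**What the plan says.** Three parts of the protocol deal with strong CYP3A inducers.

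- **Section 1.2.2** gives patient safety and lower PK variability as the reasons, and concludes that "strong inhibitors of CYPs 3A and 1A2 and strong CYP3A inducers are identified as excluded concomitant medications". It states no exception.
- **Section 6.7** opens with "The following medications and procedures are prohibited during the study". It then treats inhibitors and inducers differently. Inhibitors are not permitted, while inducers "should be avoided, unless there is no appropriate alternative medication for the patient's use". The reason given for the softer rule is that, if an interaction occurs, "MLN9708 exposure would be decreased, leading to a reduced chance of toxicity and potentially a reduced chance of efficacy". Cycle 1 is not singled out.
- **Exclusion criterion 13 (Section 5.2)** covers the period before treatment. Its list ends "carbamazepine, phenytoin, phenobarbital), or use of Ginkgo biloba or St. John's wort within 14 days before the first dose of study treatment". It does not govern use after the first dose.

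On who counts toward the MTD, Section 8.1.3 defines the DLT-evaluable population as "Patients who receive all Cycle 1 doses of MLN9708 or experience a DLT in Cycle 1" and adds: "The DLT-evaluable population will be used to determine the MTD". SAP 2.2 has the same two conditions, tied to the dose-escalation phase. Neither mentions concomitant medication.

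The main replacement rule, in Section 6.3.1, is "Patients who do not receive all doses of MLN9708 in Cycle 1 for reasons other than DLTs will be replaced within the cohort".

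**The concern.** A drug cannot be both excluded and conditionally allowed. The contrast that 6.7 draws with inhibitors suggests that the softer inducer rule was deliberate, so a site could reasonably follow it.

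The statistical problem comes from combining that rule with the DLT-evaluable definition. The protocol itself expects an inducer interaction to make toxicity less likely. A patient who starts an inducer early in Cycle 1, takes all three doses and has no DLT may have had less exposure than the assigned dose normally gives, yet enters the count as a full observation of tolerability at that dose. In a 3+3 design a level passes on 0 of 3 or 1 of 6, so one such patient can matter. The MTD is a primary endpoint, and the error can only run toward passing a level too easily.

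Elsewhere the protocol protects the Cycle 1 toxicity window. Section 6.8 disallows growth factors in Cycle 1, and Section 6.10 withholds prophylactic antidiarrheals in Cycle 1 unless there is GI amyloid. Inducers have no matching provision.

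**Working it through.** **Does any rule remove such a patient from the MTD count?**

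- *Entry.* Criterion 13 removes anyone taking a strong inducer in the 14 days before first dose. It leaves a new start on or after Day 1.
- *Evaluability.* 8.1.3 and SAP 2.2 ask only for all Cycle 1 doses or a Cycle 1 DLT. The patient qualifies.
- *Replacement.* 6.3.1 covers missed doses, and patients whose toxicity recovery is unavailable so that Cycle 1 safety cannot be fully evaluated. Section 7.9 covers patients who are not DLT-evaluable or who withdraw in Cycle 1 for reasons other than DLT. None of these names inducer use.
- *Excluded-medication condition.* 8.1.3 applies one to the PK and pharmacodynamic populations but not to the DLT-evaluable population. SAP Section 6 removes it from those two as well.
- *Deviations.* SAP 2.7 lists major deviations but says they leave the population definitions unchanged. Even under a strict prohibition, the patient would still count.

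No rule removes the patient.

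**How much could one such patient matter?**

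The plan gives no operating characteristics for the 3+3 rule and no size for the inducer effect, so there is no stated figure to reproduce. The only probabilities in Section 8.1.1 concern organ response and are not in question.

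Inputs:

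- Pass rule from Section 6.4: escalate on 0/3, or on 1/6 after 1/3.
- True DLT rate p: assumed to be 30%, 40% or 50%.
- One of the first three patients is on an inducer, with DLT risk q = p/2 (assumed).

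Formula: P(pass) = P(0 of first 3) + P(1 of first 3) × P(0 of next 3), where

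- P(0 of first 3) = (1−p)²(1−q)
- P(1 of first 3) = (1−p)²q + 2p(1−p)(1−q)
- P(0 of next 3) = (1−p)³

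With no inducer, q = p.

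Worked for p = 0.30:

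- No inducer: 0.343 + 0.441 × 0.343 = 0.494.
- One inducer patient, q = 0.15: 0.49 × 0.85 = 0.4165; 0.49 × 0.15 + 2 × 0.30 × 0.70 × 0.85 = 0.4305; 0.4165 + 0.4305 × 0.343 = 0.564.

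| True DLT rate | No inducer | One of first 3, risk halved |
|---|---|---|
| 30% | 49.4% | 56.4% |
| 40% | 30.9% | 38.6% |
| 50% | 17.2% | 24.2% |

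The shift is 7 to 8 percentage points. It depends on the assumed effect. At p = 40%, cutting that patient's risk by 25% gives 34.8%, and removing it altogether gives 46.4%. At p = 50% the corresponding figures are 20.7% and 31.2%.

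**The same check on six patients.** Section 6.4 bases the RP2D on Cycle 1 data from 6 evaluable patients. The chance of at most 1 DLT in 6, with one patient's risk halved, moves from 42.0% to 47.4% (p = 30%), 23.3% to 28.5% (40%) and 10.9% to 14.8% (50%). These are shifts of 4 to 5 points.

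**The case against.** The best reply is that the situation is rare and its effect small. Criterion 13 keeps out patients already on carbamazepine, phenytoin and the like. What remains is a patient who newly needs an inducer during Cycle 1, has no alternative, starts early enough to affect dosing on Days 1, 8 and 15, and has no DLT. If 2% of patients did so (an assumption; the documents give no rate), a cohort of three would include one with probability 1 − 0.98³, about 6%, and a 7-point shift would average about 0.4 points.

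There are also safeguards. RP2D selection weighs Grade 3/4 events, later-cycle toxicity and dose modifications. A dose level may be expanded or escalation slowed. Day 15 PK is drawn in all patients and concomitant medications are recorded, so such a patient would be visible. All of this stands and limits the size of the problem. None of it changes who is counted.

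Some stronger readings are tempting but not supported:

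- *Every inducer patient is under-exposed.* Section 6.7 makes lower exposure conditional on an interaction. Section 1.2.2 describes metabolism by several CYP and non-CYP enzymes, with CYP3A4 at 34.2% of relative activity in vitro. The case of DLT risk removed entirely is a mathematical bound, not an expectation.
- *Criterion 13 contradicts 6.7.* An entry washout and an on-study rule cover different periods and can both hold.
- *Section 6.7 permits warfarin.* Warfarin, ACE inhibitors and supplements share the bullet run under the inducer sentence, but they are not inducers and the section opens as a prohibition. This reads as a layout slip and has no bearing on the MTD.

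**Conclusion.** The conflict between 1.2.2 and 6.7, and within 6.7, stands in the current text. So does the gap in the DLT-evaluable definition: a patient who starts a strong CYP3A inducer during Cycle 1, completes dosing and has no DLT counts as tolerating the assigned dose.

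Any resulting bias is toward too high an MTD. If such a patient is among the first three at a level and the DLT risk is halved, the level's chance of passing rises by 7 to 8 points for true DLT rates of 30% to 50%. That is conditional on an uncommon event and on an assumed effect size; the documents support only the direction.

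A reader might infer that the MTD or RP2D will be set too high. The documents do not support that. They support a possible upward bias in a primary endpoint that is cheap to close, and the point is worth acting on for that reason.

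**What to change.** 1. Reconcile Sections 1.2.2 and 6.7 on whether strong CYP3A inducers may be used on study. Which rule to adopt is for the sponsor; this review does not choose one. At the same time, rearrange the 6.7 list so that warfarin, ACE inhibitors and supplements no longer sit under the inducer sentence.
2. Whichever rule is adopted, add to Protocol 8.1.3 and SAP 2.2: a patient whose strong CYP3A inducer use overlaps Cycle 1 MLN9708 dosing (started on or before the Day 15 dose) and who has no DLT is not DLT-evaluable and is replaced. A DLT in such a patient still counts.

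The asymmetry in item 2 follows the present definition, which already counts a DLT whether or not dosing was complete. The Day 15 limit avoids discarding a patient who started an inducer only after the last Cycle 1 dose.

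The cost is a wording correction, one line in each document and, rarely, one replaced patient.
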